5.4. Concomitant Medications and Medical History

5.4.1. Medical History

Medical history will be summarized for the Target mTNBC Population, mBC Population, mUC Population and the Overall Safety Population, and listed by patient. Medical history will be summarized by system organ class (SOC) and preferred term (PT) and sorted by frequency in SOC and by decreasing frequency in PT.

5.4.2. Concomitant Medications

Previous and concomitant medications will be summarized for the Target mTNBC Population, mBC Population, mUC Population and the Overall Safety Population and coded using the World Health Organization (WHO) Drug Dictionary (WHO Drug Dictionary B3 Enhanced March 2017). Medications in this section are distinct from the anticancer medications described

previously. These medications will be recorded on the “Pre-infusion medications” case report form (CRF) and the “Prior and concomitant medications” CRF rather than the “Prior Treatments” CRF. Concomitant medications are those medications that were ongoing at the time of first IMMU-132 dose or that were initiated after first dose but prior to last dose. If an end date is missing or the medication is ongoing during IMMU-132 treatment, the medication will be included as concomitant medication. Reporting of pre-treatment and concomitant medications will be by WHO Drug Anatomical Therapeutic Chemical (ATC) Classification.

Concomitant medical/surgical procedures are defined as therapies that were initiated on/after the date of the first dose of study drug and on/before the end of the study treatment period. The number (%) subjects who had concomitant medical/surgical procedures will be summarized separately in frequency tabulations.

Additional analyses or listing of concomitant medication of specific interest, if warranted in the course of safety review, may be generated.

5.5. Exposure to Study Drug and Compliance

Treatment exposure will be summarized for the Target mTNBC Population, mBC Population, mUC Population and the Overall Safety Population using the following measures:

- Number of doses administered
- Duration of treatment (months)
- Number of patients remaining on the same dose
- Number of IMMU-132 treatment cycles
- Percentage of patients with treatment delays
- Percentage of patients with dose reduction (separately for each category: Any, 1, 2 and 3 dose reductions)
- Time to first dose reduction
- Percentage of patients with permanent treatment discontinuations
- Percentage of patients with infusion interruptions but completed (based on CRF tick box information)
- Percentage of patients with infusions prematurely discontinued (based on CRF tick box information)
- Duration of patient follow-up (from start of treatment to death, last follow up, study discontinuation or data cut-off date)

Duration of treatment (in days) will be calculated as (date of the last dose – date of the first dose + 1) before being converted to months by dividing it by 30.4375. For patients who are still on treatment at the data cut-off date, the date of the last dose will be the latest dosing record end date.

Dose reductions will be calculated by taking the assigned dose level infused for each infusion (from the dose administered CRF). From this it will be possible to calculate when a dose reduction has occurred and the amount by which the dose was reduced. This will enable the dose

reduction, time to dose reduction, and number of patients with a 25% and 50% dose reduction, as outlined above to be derived.

Dose intensity is calculated by the following algorithm:

Delivered dose (in mg) for each infusion is provided per CRF form.

Delivered dosage (in mg/kg) of each infusion in a cycle is calculated by dividing the delivered dose (in mg) by body weight (in kg) at the beginning of the cycle (the body weight according to which the prescribed dose is calculated and prepared per the Protocol).

Cumulative dosage (in mg/kg) received for each subject is defined as the sum of all delivered dosage (in mg/kg) of all infusions the subject received in the study.

Total assigned dosage (in mg/kg) for each subject is defined as the product of the assigned dose (in mg/kg) and number of doses the subject was scheduled to receive during the subject's treatment period (number of infusions actually received by the subject plus the number of infusions the subject missed between the first and last infusion).

Relative dose intensity (in %) for each subject is calculated dividing the subject's cumulative dosage received (in mg/kg) by the total assigned dosage (in mg/kg) as defined above.

Patients with treatment delays longer than the 3 weeks permitted in the protocol will be summarized by number and percentage of patients. A treatment delay will have been considered to have occurred if there are >28 days between Dose 1 and Dose 2 of the same cycle, or >35 days between Dose 2 of Cycle n and Dose 1 of Cycle n+1.

In addition, exposure data will also be summarized for the subgroups as identified and defined in [Section 6.10](#) and [Section 7.1](#).

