A single whole-blood sample (purple- or pink-topped tube, 2 mL) will be collected from each registered patient prior to receiving IMMU-132 for determination of UGT1A1 and related genotypes. This sample will be shipped to Sponsor who will perform this assay. The results from this test are NOT required to determine eligibility but will be used retrospectively to assess its utility in predicting toxicity.

 PPD

 Core biopsies that are  fresh-frozen and also formalin-fixed (described above) are also desired at baseline and intervals during therapy whenever possible.

In the ongoing Phase II study, all patients receive IMMU-132 10 mg/kg administered in 3-week treatment cycles with weekly dosing the first two weeks (days 1 and 8 of 21-day cycles) and no dosing the third week. The cycles are to be continued in the absence of unacceptable toxicity or progression of disease requiring termination of further treatment. The first assessment of disease progression per RECIST1.1 does not require discontinuation of study treatment if there is still the potential for patient benefit in the opinion of the investigator and approved by the Sponsor, but treatment must be discontinued if subsequent imaging documents disease progression from that assessment.

All patients are closely monitored over the course of their treatment, and NCI CTCAE v4.0 is used to grade all adverse events and to provide dose reduction, delay or cessation guidelines in the event of treatment-related toxicity. Based on irinotecan and animal testing, the major toxicity of IMMU-132 is expected to be gastrointestinal symptoms and hematologic suppression. Growth factors and other supportive care are allowed when medically necessary any time during treatment with IMMU-132 but should not be given prophylactically before start of treatment with IMMU-132 first dose in cycle 1.

In the current experience in over 200 patients, the major Grade 3 or Grade 4 toxicity has been neutropenia, which is managed with dose delay, dose reduction, or growth factors, if spontaneous remission is not experienced within 7 days.

CCI

CCI

Patients who exhibit an excessive cholinergic response to IMMU-132 treatment (e.g., abdominal cramping, diarrhea, salivation, etc.) can receive appropriate premedication (e.g., atropine) for subsequent treatments.

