6.8. Criteria for Removal from Protocol Treatment

Patients may be removed from protocol treatment under the following conditions:

- First documentation of progressive disease (Physician discretion and Sponsor approval to continue) or symptomatic deterioration indicating treatment failure.
- Patients who want to continue treatment after radiological documentation of progressive disease should notify the physician who will obtain Sponsor approval before treatment continuation.
- Unacceptable toxicity.
- Treatment delay for any reason > 3 weeks (Treatment delays of up to 3 weeks will be allowed at the investigator's discretion).
- The patient may withdraw from the study at any time for any reason.

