7.4.5. Dosing Schedule

[figure not shown]
All patients receive IMMU-132 to be administered in the ongoing Phase II study at 10 mg/kg weekly for 2 consecutive weeks (2 weekly doses plus 1 week without treatment represents a single 3 week cycle). Treatment can be continued without a rest period in the absence of progression of disease or unacceptable toxicity. Planned deviations in treatment schedule are allowable up to 7 days due to holidays, vacations or personal reasons.

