5. STATISTICAL ANALYSES

Throughout this SAP, efficacy data will be summarized for the Target mTNBC Population, mBC, mUC, SCLC, NSCLC, CRC, EGC, EMC and PDC Population, with all patients in the respective population combined, while safety data will be summarized for the Target mTNBC Population, mBC Population, mUC Population and the Overall Safety Population. For the Overall Safety Population, data will be summarized by dose group (defined as assigned dose) and overall.

All data will be listed for the Overall Safety Population and where applicable, in the cancer-specific analysis population, as specified.

Screen failures and entered-but-not-dosed patients will be excluded from all analyses.

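### SAP 5.5 computes relative dose intensity without elapsed time and counts delays only beyond 21 days, so protocol-permitted delays can leave reported intensity at 100%

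*SAP*

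**What the plan says.** SAP 5.5 introduces an algorithm for dose intensity. Delivered mg/kg is summed over all infusions. The total assigned dosage is the assigned mg/kg times the number of doses scheduled during the patient's treatment period, and a parenthesis spells that number out as the "number of infusions actually received by the subject plus the number of infusions the subject missed between the first and last infusion". RDI is then "calculated dividing the subject's cumulative dosage received (in mg/kg) by the total assigned dosage (in mg/kg) as defined above". No dose per week is defined.

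Delays appear twice in the same section. The list of exposure measures includes "Percentage of patients with treatment delays", with no threshold in that line. After the RDI formula the SAP adds: "Patients with treatment delays longer than the 3 weeks permitted in the protocol will be summarized by number and percentage of patients". It then defines a delay as more than 28 days from Dose 1 to Dose 2 of a cycle, or more than 35 days from Dose 2 to Dose 1 of the next cycle.

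On the protocol side:

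- Section 6.8: "Treatment delays of up to 3 weeks will be allowed" at the investigator's discretion.
- Section 7.4.5: "Planned deviations in treatment schedule are allowable up to 7 days due to holidays, vacations or personal reasons".
- Section 6.4: a window of plus or minus 1 day around Days 1 and 8.
- Synopsis, Study Design: "the major Grade 3 or Grade 4 toxicity has been neutropenia, which is managed with dose delay, dose reduction, or growth factors".

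**The concern.** Dose intensity is normally read as drug delivered per unit time relative to plan. The SAP's ratio is relative cumulative dose: a full-dose infusion adds the same amount to numerator and denominator however late it is given. The defined delay row then starts exactly where the protocol's permission ends. A delay the protocol allows can therefore escape both measures.

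Safety is part of the Phase II primary objective, and delay is one of the tolerability signals this trial itself used. Protocol Section 1 records that the 12 mg/kg starting dose was set aside because 8 of 9 patients needed delays and reductions in the first cycle. The exposure tables cover the Target mTNBC, mBC, mUC and Overall Safety Populations; for the last, "data will be summarized by dose group (defined as assigned dose) and overall". A clinical study report could state near-complete delivery of the Day 1 and Day 8 schedule for patients who received materially less drug per week.

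**Working it through.** **Inputs.** Planned gaps are 7 and 14 days in a 21-day cycle at 10 mg/kg per infusion (Protocol 7.4.5). Permitted delay is up to 21 days (Protocol 6.8). The RDI formula and the 28- and 35-day rules are in SAP 5.5.

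**The SAP's delay thresholds.** 28 − 7 = 21 and 35 − 14 = 21, so both rules match the protocol limit. A Dose 2 to Dose 1 gap exactly 21 days late is 35 days, which is not more than 35, so it is not counted; 22 days late is counted.

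**Example patient.** Full doses, no infusion missed, each new cycle starting d days late.

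- SAP RDI over six cycles, with a late infusion not counted as missed: (12 × 10) / (10 × (12 + 0)) = 100% for any d.
- Dose per unit time, per cycle: 21 / (21 + d). Weekly dose: 20 × 7 / (21 + d), against a planned 6.67 mg/kg.
- Six cycles, first to last infusion: scheduled 5 × 21 + 7 = 112 days; actual 112 + 5d days.
- Original-calendar reading: infusions that the undelayed calendar would have placed up to the actual last infusion day are 15, 18 and 22 for d = 7, 14 and 21. RDI is 12 divided by that number.

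| Delay per cycle | SAP RDI, late not missed | In the >3-week row? | Per-cycle ratio | mg/kg per week | Six-cycle ratio | RDI, original calendar |
|---|---|---|---|---|---|---|
| 7 days | 100% | No | 21/28 = 75% | 5.00 | 112/147 = 76% | 12/15 = 80% |
| 14 days | 100% | No | 21/35 = 60% | 4.00 | 112/182 = 62% | 12/18 = 67% |
| 21 days | 100% | No | 21/42 = 50% | 3.33 | 112/217 = 52% | 12/22 = 55% |

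**Effect of the unclear word.** For the 7-day case the same SAP text yields 100% or 80%, depending on how missed infusions are counted.

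**Effect on a population mean.** The documents give no Phase II delay rate, so this is an assumption. If a share f of patients ran 7 days late every cycle for six cycles and the rest were on time, mean RDI would be overstated by (100 − 76.2) × f = 23.8 × f points: about 5, 12 or 19 points for f = 20%, 50% or 80%.

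**The case against.** The strongest reply is that the 100% figure depends on a reading. The SAP speaks first of doses scheduled during the treatment period. If missed infusions are counted against the original calendar, RDI comes out at 80%, 67% or 55%, within 3 to 5 points of the six-cycle time-based ratio. That is fair. However, the parenthesis gives a count of received plus missed infusions, and nothing says that a postponed infusion is a missed one.

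Second, other outputs show part of the picture. Treatment duration, doses and cycles are summarised; SAP 7.1 tabulates AEs and AESIs leading to interruption, and AESI durations; all data are listed. But separate summaries do not give a per-patient ratio. The same 12 infusions would show as (112 + 1)/30.4375 = 3.7 months on schedule and (217 + 1)/30.4375 = 7.2 months with 21-day delays, and a reader could take the longer figure for better persistence.

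Third, the dose-modification rules in Protocol 7.4.6 are redacted. They may force a reduction after repeated delays, so the patient who is late every cycle at full dose may be rare. This limits how often the problem occurs; it does not alter the formula.

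Three stronger readings are tempting, and the documents do not support them:

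- *That the SAP leaves treatment delay undefined.* SAP 5.5 gives a numeric rule. What is open is whether the bullet on treatment delays uses that rule, in which case shorter delays are never counted, or is meant more widely, in which case its threshold is not in the readable SAP. It may be in the programming specification named in SAP 10.
- *That delay is the usual response to neutropenia.* The synopsis lists delay, reduction and growth factors without ranking them. Reduction does lower RDI and is reported.
- *That RDI would show 10 mg/kg as a higher exposure than 8 mg/kg.* RDI is a percentage of each patient's own assigned dose, so full doses give 100% in both groups. The SAP plans no mg/kg-per-week figure that would rank them.

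**Conclusion.** The point stands as a defect in a descriptive exposure measure. On the SAP's literal count, and provided a postponed infusion is not recorded as missed, delays within the protocol's 3-week limit leave RDI unchanged and fall outside the defined delay row. In the worked case RDI overstates dose per unit time by 25, 40 or 50 percentage points per cycle (24, 38 or 48 over six cycles from first to last infusion). On the calendar reading the overstatement falls to about 4, 5 or 3 points, and the defect is mainly one of ambiguity.

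How much the reported means would move cannot be determined from the documents. No hypothesis test is planned, and ORR, PFS, OS and the selected dose are unaffected. What is at risk is the statement in the report about how fully the schedule was delivered and tolerated. Because the data needed are already used in SAP 5.5, the change is worth making.

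**What to change.** In SAP 5.5:

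1. Report RDI as the present ratio × (scheduled days from first to last infusion / actual days from first to last infusion). Count scheduled days over received plus missed infusions, and set the factor to 1 for a patient with one infusion. Keep the present ratio as a separate row named relative cumulative dose.
2. State that a late infusion is not a missed infusion. Without this, the time factor and a calendar count would penalise the same delay twice (7-day case: 0.80 × 0.762 = 0.61 instead of 0.76).
3. For the percentage of patients with treatment delays, define delay as the actual gap minus the scheduled gap. Report any delay beyond the 1-day window in four categories: up to 7 days, >7 to 14, >14 to 21, and >21 days. Footnote that the lowest category and the time factor include the planned deviations of up to 7 days allowed by Protocol 7.4.5.

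The cost is a revised definition, one clarifying sentence and a few table rows, from infusion dates and doses already collected. No protocol change is needed. The drawback is a somewhat less favourable RDI that also reflects scheduling delays unrelated to toxicity; the retained cumulative-dose row lets the reader separate dose reduction and omission from lateness.

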3. INVESTIGATIONAL PLAN

3.1. Overall Study Design and Plan

IMMU-132-01 is a Phase I/II, open-label, basket design study of IMMU-132 in adult patients with epithelial cancers expressing Trop-2. The allowed cancer types include ovarian, endometrial, cervical, breast (Triple-Negative Breast Cancer [TNBC] and non-TNBC), prostate (hormone refractory), lung (non-small cell and small-cell lung [NSCLC and SCLC], head and neck (squamous cell), esophageal, gastric, hepatocellular, renal (clear cell), thyroid, glioblastoma multiforme, colorectal, pancreatic, and urothelial cancers (UC). Eligible patients were required to have metastatic (Stage IV) disease at the time of study entry (except for glioblastoma multiforme) and be refractory to or have relapsed after at least 1 prior standard therapeutic regimen for their disease. All patients received IMMU-132 administered IV as a single agent in 3-week treatment cycles (Days 1 and 8 of 21-day cycles). Patients were to continue treatment until disease progression requiring discontinuation of treatment or unacceptable toxicity. A protocol-defined dose reduction scheme was in place to manage patients with selected AEs.

The primary objective of Phase I is to evaluate the safety and tolerability of IMMU-132 in patients with advanced epithelial cancers, using a dose escalation design to determine the maximum acceptable dose. The secondary objective of Phase I is to evaluate the PK, immunogenicity, and preliminary efficacy of IMMU-132. The primary objective of Phase II is the evaluation of the safety and efficacy of IMMU-132 at a dose selected in Phase I, while the secondary objectives of Phase II also include evaluation of PK and immunogenicity.

Screening/baseline procedures include patient history, physical examination with vital signs and performance status evaluation, local histology/pathology review to confirm 1 of the epithelial cancers listed above, safety laboratory assessments, and electrocardiogram (ECG). Tumor imaging was performed using contrast enhanced computed tomography (CT) or magnetic resonance imaging (MRI). Baseline imaging was obtained within 4 weeks of study entry. Blood/samples were collected to test for human anti-human antibody (HAHA), and uridine diphosphate glucuronosyltransferase 1A1 (UGT1A1) genotype CCI

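### The SAP 5.5 treatment-delay rule has no test for a gap that spans an omitted infusion, so the percentage of patients delayed by more than 3 weeks can be undercounted

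*SAP*

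**What the plan says.** The dosing schedule in SAP 3.1 is "3-week treatment cycles (Days 1 and 8 of 21-day cycles". Protocol 6.8 lists "Treatment delay for any reason > 3 weeks" among the conditions under which a patient may be taken off treatment, and adds that "Treatment delays of up to 3 weeks will be allowed at the investigator's discretion".

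SAP 5.5 turns that limit into an exposure measure: "Patients with treatment delays longer than the 3 weeks permitted in the protocol will be summarized by number and percentage of patients". It then defines a delay by two intervals: ">28 days between Dose 1 and Dose 2 of the same cycle, or >35 days between Dose 2 of Cycle n", where the second interval ends at the first infusion of the following cycle. It gives no other interval and no fallback to a planned date.

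The same section allows for infusions that were not given. The denominator of relative dose intensity is built from the infusions received "plus the number of infusions the subject missed between the first and last infusion".

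Exposure is summarised for the Target mTNBC, mBC, mUC and Overall Safety Populations (SAP 5.5). SAP 5 adds a breakdown by dose group for the Overall Safety Population.

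**The concern.** Both intervals need a Dose 2 date. When the Day 8 infusion of a cycle was omitted, neither can be computed for the gap up to the next cycle. The mirror case has the same hole: if Dose 1 of a cycle was omitted and Dose 2 given, the gap back to the previous cycle's Dose 2 has no test.

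The measure is meant to show how many patients went beyond the delay the Protocol permits, and it bears on tolerability. Two patients who restart on the same late date are treated differently: the one who received Day 8 is counted, and the one who did not is not. The deviations listed for programming in SAP 8 do not include delay, so no other stated summary is aimed at this limit.

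**Working it through.** **Inputs.** Infusions on Days 1 and 8 of a 21-day cycle (SAP 3.1); 21 days of permitted delay (Protocol 6.8); limits of 28 and 35 days (SAP 5.5).

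**Reproducing the plan's limits.** Limit = scheduled interval + 21 days.
- Dose 1 to Dose 2: (8 − 1) + 21 = 28. Matches.
- Dose 2 to next Dose 1: (22 − 8) + 21 = 35. Matches.
- Dose 1 to next Dose 1, or Dose 2 to next Dose 2: 21 + 21 = 42. The SAP has no such test.

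**Applying the rule as written.** Cycle 1 Dose 1 is on study day 1. Day 8 is either given or omitted. Cycle 2 Dose 1 was due on day 22, and later doses run on schedule from the date it was given.

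| Cycle 2 Dose 1 on day | Days late | Gap from Dose 2 (day 8), if given | SAP rule, Day 8 given | Gap from Dose 1 (day 1) | SAP rule, Day 8 omitted | With the >42-day test, Day 8 omitted |
|---|---|---|---|---|---|---|
| 22 | 0 | 14 | no | 21 | no | no |
| 43 | 21 | 35 | no | 42 | no | no |
| 44 | 22 | 36 | yes | 43 | no | yes |
| 64 | 42 | 56 | yes | 63 | no | yes |
| 100 | 78 | 92 | yes | 99 | no | yes |
| 200 | 178 | 192 | yes | 199 | no | yes |

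With Day 8 omitted, the rule flags nothing even at 178 days late. The added test puts the cut-point at day 44, the same day as when Day 8 was given.

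**The same patient through another cycle.** Cycle 1 Day 8 omitted, Cycle 2 doses on days 100 and 107, Cycle 3 Dose 1 on day 150. The last gap is 150 − 107 = 43 days, which exceeds 35, so the patient is counted. The omission removes one gap from view, not the patient.

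**If the next infusion is labelled Dose 2 of Cycle 1.** Given on day 30, its gap is 29 days, which exceeds 28, so it is flagged. Against the Day 8 due date it is 29 − 7 = 22 days late, so the flag is right under that label. Labelled as Cycle 2 Dose 1 (due day 22), the same infusion is 30 − 22 = 8 days late. The result depends on the recorded dose position and on the due date used.

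**Effect of one missed patient.** In the Target mTNBC Population of 108 (SAP 4) it is 1/108 = 0.9 percentage points. In the Overall Safety Population of about 495 it is 1/495 = 0.2 percentage points.

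**The case against.** The best reply is that this is a wording gap in one descriptive line, and that few patients may fall into it. To be missed, a patient must omit an infusion, restart more than 21 days late, and have no other flagged gap. A delay over 3 weeks is itself a listed removal condition, and a patient removed for it has no later infusion, so neither the current nor the amended rule yields an interval. All of that stands, and it limits the size. It does not empty the category: Protocol 6.8 says patients may be removed, so a late restart remains possible.

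A fallback may also exist out of sight. SAP 10 assigns programming details to a separate specification, and part of Protocol 7.4.6 is redacted. However, SAP 5.5 gives an explicit definition rather than a placeholder, and no visible text repairs it.

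Some of the lost information appears elsewhere. Missed infusions lower relative dose intensity, adverse events leading to dose interruption are tabulated (SAP 7.1), and the data are listed. None of these reports the length of a delay.

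A reader might infer more than the documents support:
- That a patient with an omitted Day 8 can never be counted. Another cycle can still flag the patient.
- That the reported percentage is certainly too low. Undercounting is possible under the literal reading; it is not shown to have occurred.
- That the affected patients are mainly those with toxicity. This is plausible, but Protocol 6.8 covers delay for any reason and the reasons for omissions are not given.
- That every tumour cohort is affected. Table 2 of the SAP plans no exposure summary for SCLC, NSCLC, CRC, EGC, EMC or PDC.
- That an assumed omission rate gives the number misclassified. If 5% to 20% of about 495 patients omitted a Day 8 infusion (an assumption without a source), 25 to 99 would have an untested gap. Only those who also restarted late and were not flagged elsewhere would be miscounted.

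**Conclusion.** The point holds as a minor defect in an analysis definition. The SAP's two limits are correct where both infusions of a cycle were given, but the rule has no test for a gap that spans an omitted infusion. Followed literally, it can undercount patients delayed by more than 3 weeks in the four populations with an exposure summary. The size cannot be estimated from the documents and may be small. ORR, PFS, OS and the other efficacy endpoints are untouched.

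The conclusion assumes that the unseen programming specification adds no fallback and that infusions keep their recorded cycle and dose position. The 42-day figure extends the SAP's own arithmetic. It is not a reading of Protocol 6.8, whose visible text does not say from which due date a delay runs after an omission.

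**What to change.** In SAP 5.5, replace the two tests with one, applied to every pair of consecutive infusions actually given, using the recorded cycle and dose position: flag a delay over 3 weeks when the actual interval minus the scheduled interval between those two positions exceeds 21 days. Show the resulting limits:
- >28 days, Dose 1 to Dose 2 of the same cycle (unchanged);
- >35 days, Dose 2 to Dose 1 of the next cycle (unchanged);
- >42 days, Dose 1 to next-cycle Dose 1, or Dose 2 to next-cycle Dose 2, when the infusion between was omitted (new).

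State that the delay is counted from the planned date of the infusion actually given, and check this against the programming specification. If a fallback already exists there, a cross-reference and agreement between the two texts are enough.

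The change concerns the analysis definition only and leaves the Protocol's treatment rules as they are. It costs a short addition to the SAP and a small programming change, and needs no new data. The reported delay percentage may rise slightly.
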